7.2.2 Handling of Intercurrent Events

The expected intercurrent events of interest in this trial are:

- Start of a product with a similar mode of action as trial medication that has proven efficacy (either preliminary via EUA by FDA or via full approval by the FDA or EMA)
- Start of a restricted medication as defined in Table 4.2.2.1:1, except any product with a similar mode of action as trial medication that has proven efficacy (either preliminary via EUA by FDA or via full approval by the FDA or EMA)
- Death

The strategies for handling intercurrent events in this trial are as follows:

Primary strategy: This is the effect of randomising a patient to a treatment, but excluding the effects of any other products with a similar mode of action as trial medication that have proven efficacy (either preliminary via EUA by FDA or via full approval by the FDA or EMA). Start of a restricted medication as defined in Table 4.2.2.1:1, except any product with a similar mode of action as trial medication that has proven efficacy (either preliminary via EUA by FDA or via full approval by the FDA or Via full approval by the FDA or EMA) will be handled using the treatment policy approach as defined in ICH E9(R1). Death will be handled using the composite approach as defined in ICH E9(R1). The use of any other products with a similar mode of action as trial medication that have proven efficacy will be handled using the while-on-treatment approach as defined in ICH E9(R1), with the treatment period defined as the period from first administration of randomised medication to the end of the residual effect period or to the start of the intercurrent event, whichever occurs first.

Secondary strategy: This strategy is similar to the primary strategy, except for the intercurrent event "use of any other products with a similar mode of action as trial medication that have

Boehringer Ingelheim		
BI Trial No.: 1487-0001		20 Apr 2021
c33563257-02	Clinical Trial Protocol	Page 86 of 127

proven efficacy (either preliminary via EUA by FDA or via full approval by the FDA or EMA)", which will be handled using the composite approach as defined in ICH E9(R1).

Table 7.2.2:1 provides an overview of the handling of intercurrent events within the different strategies.

Intercurrent Event	Strategy for handling of intercurrent events	
	Primary strategy	Secondary strategy
Start of a product with a similar mode of action as trial medication that has proven efficacy (either preliminary via EUA by FDA or via full approval by the FDA or EMA).	While-on-treatment	Composite
Start of a restricted medication as defined in Table 4.2.2.1:1 , except any product with a similar mode of action as trial medication that has proven efficacy (either preliminary via EUA by FDA or via full approval by the FDA or EMA)	Treatment policy	Treatment policy
Death	Composite	Composite

Table 7.2.2:1 Handling of intercurrent events as per ICH E9(R1) within the different strategies

Each analysis will reference the strategy for handling intercurrent events that it will be estimating. The estimand for each main analysis in this protocol is the combination of the relevant detailed clinical objective from Section 2.1 and this strategy.

The handling of intercurrent events that are not listed will be decided during blinded review and will be documented in the TSAP.

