	Confirmatory Phase III: Confirmatory, randomised, double-blind, placebo-controlled, parallel group, Phase III comparing BI 767551 to placebo. Patients will be randomised in a 1:1 ratio to receive a single i.v. or inhaled dose of study treatment or placebo followed for 90 days of follow up. In addition, randomisation will be stratified by "high" versus "low" risk of progresson to COVID-19 to ensure equal distribution between treatment arms. The study will have a group-sequential design including two interim analyses that will be performed by the DMC. These analyses encompass futility and efficacy. Only the DMC will have access to unblinded data during this portion of the study.						
Total number of patients randomised	Phase II: approximately 200 patients to be randomised. Phase III: approximately 1300 patients to be randomised.						
Number of patients per treatment group	 Phase II approximately: Placebo i.v. + Placebo inhaled: 50 patients BI 767551 i.v. 10 mg/kg + Placebo inhaled: 50 patients BI 767551 i.v. 40 mg/kg + Placebo inhaled: 50 patients Placebo i.v. + BI 767551 inhaled: 50 patients Phase III approximately: BI 767551 i.v. 700 mg or 2800 mg: 650 patients or BI 76551 250 mg inhaled and Placebo: 650 patients 						
Diagnosis	COVID-19 detected by SARS-CoV-2 positive test confirmed by RT- qPCR or antigen test.						
Main inclusion and exclusion criteria	 Eligibility criteria for Phases II and III are identical. Patients participating in Phase II are not eligible for Phase III. Main criteria for inclusion: Age ≥ 18 years old, males and females. Signed and dated written informed consent in accordance with ICH-GCP and local legislation prior to admission to the trial. Documentation of laboratory-confirmed SARS-CoV-2 infection, as determined by a molecular test (antigen or nucleic acid) from any respiratory tract specimen (NP or nasal swab or saliva) collected no more than 72 hours prior to start of treatment. Patients experienced mild to moderate COVID-19-related symptoms or measured fever for no more than 5 days prior to 						

BI Trial No.: 1487-000 c33563257-02	1 Clinical Trial Pro	20 Apr 2021 Page 5 of 127
Proprietary confidential informa	ion © 2021 Boehringer Ingelheim Interr	national GmbH or one or more of its affiliated companies

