4.2 OTHER TREATMENTS, EMERGENCY PROCEDURES, RESTRICTIONS

4.2.1 Other treatments and emergency procedures

Stable doses of concomitant therapies for chronic conditions, for which neither the condition nor the treatment are judged to exclude the patient from participation (see Section 3.3), are permissible. In case of adverse event in need of treatment, symptomatic therapy according to investigator judgement will be permitted.

Infusion reaction

In case of an acute infusion reaction, the infusion will be interrupted and not be re-initiated. For infusion reactions requiring medical intervention, rescue medication including, but not limited to, acetaminophen/paracetamol, antihistamines, glucocorticoids, and IV fluids must be available on site.

Inhalation reaction

In case of bronchial hyperresponsiveness (e.g., bronchospasm), bronchodilators and/or antiinflammatory medications may be provided by inhalation or intravenously as deemed clinically appropriate.

Rescue treatment

During the trial, if COVID-19 worsens, the patient can be treated with medications at the discretion of the investigator (refer to Restricted medication Table 4.2.2.1:1, footnote 2) as per local guidelines. Any additional investigational products related to COVID-19 could be given for COVID-19 disease worsening, after Day 2 at the discretion of the investigator but may require additional safety monitoring by the site.

All efforts should be made to inform the patient of the importance of completing the protocol specified visits (See Flow Chart) up to Visit 9. Patients refusing to complete the scheduled visits after the day of treatment should at least provide safety information by phone at the respective visits.

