7.1 NULL AND ALTERNATIVE HYPOTHESES

In Phase II, no confirmatory testing is performed and hence no null and alternative hypotheses are defined. All p-values are to be understood as exploratory. A justification of the sample size is provided in Section 7.5.1.

In Phase III, the superiority of BI 767551 compared to placebo will be tested for the proportion of patients hospitalized or who died from any cause by Day 29.

The null hypothesis is:

H0: The probability to get hospitalized or to die by Day 29 in the BI 767551 arm is equal to the probability to get hospitalized or to die by Day 29 in the placebo arm.

The alternative hypothesis is:

H1: The probability to get hospitalized or to die by Day 29 in the BI 767551 arm is smaller than the probability to get hospitalized or to died by Day 29 in the placebo arm.

The control of the global overall significance level of 2.5% (one-sided) is assured for the primary endpoint as follows: Adjustments accounting for the planned interim analyses are done using the Lan-DeMets spending function approach with an O'Brien and Fleming boundary. For the primary endpoint, statistical significance will be declared (either at one of the interim analyses or in the final analysis) if the analysis is significant at the local nominal one-sided alpha level. These O'Brien and Fleming local nominal one-sided alpha levels are given in Table 7.5.2:1 for each interim and the final analysis for the planned information fraction. The one-sided p-value is required for the primary endpoint due to the use of a group sequential design.

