7.3 HANDLING OF MISSING DATA

7.3.1 Efficacy endpoints

For the analysis of the primary endpoint of Phase II and of other continuous endpoints, missing data will not be imputed. For continuous endpoints analysed using a MMRM, the mixed effect model will handle missing data based on a likelihood method under the "missing at random assumption".

For the analysis of the primary endpoint of the Phase III and of other time-to-event endpoints or endpoints assessing the occurrence of an event by a pre-defined timepoint, missing or incomplete data will not be imputed but will be handled using standard survival analysis techniques (i.e. censoring). For the primary analysis of the primary endpoint the censoring rules are outlined in Table 7.3.1:1.

Proprietary confidential information © 2021 Boehringer Ingelheim International GmbH or one or more of its affiliated companies

Table 7.3.1: 1Censoring Rules for the primary analysis of the primary endpoint of
Phase III

Rule #	Situation	Outcome (event or censored)	Date of event or censoring
1	Patient has been hospitalized or has died within the first 29 days and date of hospitalization or death is known	Event	Date of event
2	Patient has been hospitalized or has died within the first 29 days and date of hospitalization or death is unknown	Event	Imputed date of event: 1 day after the date of last contact when the patient is known to be alive and not hospitalized
3	Patient is alive and has not been hospitalized within the first 29 days	Censored	Day 29
4	Patient is alive and has not been hospitalized within the first 29 days but has started within the first 29 days another drug with a similar mode of action as study treatment that has proven efficacy (either preliminary via EUA by FDA or via full approval by the FDA or EMA).	Censored	Start date of drug with similar mode of action
5	Unknown	Censored	Date of last contact when the patient is known to be alive and not hospitalized

Censoring rules for secondary or

further endpoints will also be provided in the TSAP.

For the analysis of the categorical endpoints, missing data will be imputed using the worst

case. Further details will be provided in the TSAP. For further endpoints, handling of missing data will be described in the TSAP.

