7.5.2 Determination of sample size for Phase III

In Phase III, with a sample size of 641 per treatment group, the study has 80% power to detect a relative reduction of 50% in the proportion of patients hospitalized or dying over 29 days between the study groups (BI 767551 vs. placebo), using the following assumptions:

- There are limited data available on the treatment effect and variability for the primary endpoint. Based on recent publications, the proportion of patients who get hospitalized or die over 29 days in the placebo arm is assumed to be 7.5%.
- Two interim analyses and one final analysis, with stopping guideline for efficacy of BI 767551 versus placebo determined using the Lan-DeMets spending function approach with an O'Brien and Fleming boundary.

Table 7.5.2:1 summarizes the details of such a design.

Table 7.5.2:1 Design details and sample size calculation for a group sequential design in Phase III

Assuming that only a low number of patients might be lost to follow up, it is planned to randomise approximatively 1300 patients in Phase III.

8. INFORMED CONSENT, TRIAL RECORDS, DATA PROTECTION, PUBLICATION POLICY, AND ADMINISTRATIVE STRUCTURE

The trial will be carried out in compliance with the protocol, the ethical principles laid down in the Declaration of Helsinki, in accordance with the ICH Harmonized Guideline for Good Clinical Practice (GCP), relevant BI Standard Operating Procedures (SOPs), the EU directive 2001/20/EC / EU regulation 536/2014 and other relevant regulations. Investigators and site staff must adhere to these principles. Deviation from the protocol, the principles of ICH GCP or applicable regulations as will be treated as "protocol deviation". Standard medical care (prophylactic, diagnostic and therapeutic procedures) remains the responsibility of the treating physician of the patient.

The investigator will inform the sponsor or delegate immediately of any urgent safety measures taken to protect the trial patients against any immediate hazard, as well as of any serious breaches of the protocol or of ICH GCP.

The Boehringer Ingelheim transparency and publication policy can be found on the following web page: trials.boehringer-ingelheim.com. The rights of the investigator and of the sponsor with regard to publication of the results of this trial are described in the investigator contract. As a rule, no trial results should be published prior to finalisation of the CTR.

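### Phase III names a while-on-treatment strategy for starting another antibody but applies Kaplan-Meier censoring, which targets a different risk and is informative because permitted starts follow worsening

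*Protocol*

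**What the plan says.** **Objective and strategy.** Protocol Section 2.1.1 bases the Phase III primary comparison on all randomised patients, using data up to the start of any other proven product with a similar mode of action. Section 7.2.2 names the strategy: "The use of any other products with a similar mode of action as trial medication that have proven efficacy will be handled using the while-on-treatment". Table 7.2.2:1 repeats the label. The opening of the same paragraph, however, defines the primary strategy as the effect of randomisation with the effects of such products taken out. A secondary strategy treats the same intercurrent event as composite.

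**Estimator.** Section 7.2.3 estimates the Day 29 proportion hospitalised or dead by Kaplan-Meier, stratified by risk of progression and baseline serology. On incomplete data Section 7.3.1 says "missing or incomplete data will not be imputed but will be handled using standard survival analysis techniques (i.e. censoring"). In Table 7.3.1:1, rule 4 sets the censoring date for a starter who is event-free through Day 29 as "Start date of drug with similar mode of action". Rule 1 counts any hospitalisation or death in the first 29 days, with no exception for an earlier start.

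**When a start is permitted.** Table 4.2.2.1:1 bars other SARS-CoV-2 antibodies from Visit 2 to Day 29. Only two footnotes attach to that row: footnote 2 (COVID-19 worsening, pointing to Section 4.2.1) and footnote 3 (rescue use). Footnote 1, for conditions other than COVID-19, does not. Section 4.2.1 says: "During the trial, if COVID-19 worsens, the patient can be treated with medications at the discretion of the investigator".

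**SAP.** It covers Phase II only and adds nothing on this analysis.

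**The concern.** Three descriptions of one estimand do not agree.

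- **While-on-treatment** asks how many patients are hospitalised or die before starting another product. A patient who starts first is a non-event, so start acts as a competing event.
- **The effect with other products removed** asks what the Day 29 risk would have been had nobody started one. That is a hypothetical strategy.
- **Kaplan-Meier with censoring at start** gives each censored patient the later risk of those still under observation. It estimates the hypothetical risk only if starters and non-starters have the same prognosis.

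The protocol's rescue rule breaks that last condition. Someone permitted to start has just deteriorated, yet is analysed as having the average remaining risk of the stratum. Risk group and serology are fixed at baseline and cannot account for later worsening.

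At stake are the meaning of the reported primary effect, some understatement of the absolute difference relative to the hypothetical target, and some power. Both Phase III interim decisions rest on the same estimate.

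**Working it through.** **Plan figure first.** Section 7.5.2 says that "with a sample size of 641 per treatment group, the study has 80% power to detect a relative reduction of 50"%, and that "the proportion of patients who get hospitalized or die over 29 days in the placebo arm is assumed to be 7.5"%. So p is 7.5% on placebo and 3.75% on active, a difference of 3.75 points. On the log-risk-ratio scale:

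- v = 0.925/0.075 + 0.9625/0.0375 = 12.33 + 25.67 = 38.0
- standard error = √(38.0/641) = 0.2435
- ln 2 / 0.2435 = 2.847
- with a final O'Brien-Fleming critical value of about 1.99, power = Φ(0.857) ≈ 80%

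The plan's figure reproduces. Table 7.5.2:1 is not visible, so the exact variant used cannot be confirmed.

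**Assumptions (the documents give none of these).**

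- A fraction f of would-be events in each arm is preceded by a start one day earlier.
- A fraction g = 2% of other patients also start, evenly over Days 2 to 28.
- Events fall evenly over Days 3 to 16.
- The rescue product prevents a share e of the events it precedes.

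**Formula.** Let φ be the share of would-be events lost to censoring. If every starter is censored, φ = f. Under rules 1 and 4 as worded, events after a start still count, so φ = f × e. Observed incidence is q = p(1 − φ). Kaplan-Meier adds the average remaining risk for each censored patient. The mean share of the event window still ahead is 7.5/14 = 0.536 for would-be-event starters and 7.5/27 = 0.278 for the others (7.5 = (14 + 13 + … + 1)/14):

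KM risk ≈ q × [1 + 0.536 φ p + 0.278 g (1 − p)]

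Example with φ = 0.20:

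- placebo: 6.00 × [1 + 0.0080 + 0.0051] = 6.08
- active: 3.00 × [1 + 0.0040 + 0.0054] = 3.03

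| Case | φ | Placebo % | Active % | Difference | Ratio |
|---|---|---|---|---|---|
| No starters | 0 | 7.50 | 3.75 | 3.75 | 0.50 |
| All starters censored, f = 10% | 0.10 | 6.81 | 3.40 | 3.41 | 0.50 |
| All starters censored, f = 20% | 0.20 | 6.08 | 3.03 | 3.05 | 0.50 |
| As worded, e = 50%, f = 10% | 0.05 | 7.18 | 3.59 | 3.59 | 0.50 |
| As worded, e = 50%, f = 20% | 0.10 | 6.81 | 3.40 | 3.41 | 0.50 |
| As worded, e = 0, any f | 0 | 7.54 | 3.77 | 3.77 | 0.50 |

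**Gap to the named strategy.** While-on-treatment incidence is p(1 − f).

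- f = 10%: 6.75 − 3.375 = 3.375 points
- f = 20%: 6.00 − 3.00 = 3.00 points

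With every starter censored, Kaplan-Meier is above this by 3.41 − 3.375 ≈ 0.04 and 3.05 − 3.00 = 0.05 point. As worded with e = 50%, it is above by 3.59 − 3.375 ≈ 0.22 and 3.41 − 3.00 = 0.41 point. That larger gap comes from rule 1 counting events after a start.

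**Power.** For f = 20% with every starter censored:

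- v = 0.9392/0.0608 + 0.9697/0.0303 ≈ 47.4, so the standard error is 0.272
- ln(6.08/3.03)/0.272 ≈ 2.56, so power = Φ(0.57) ≈ 72%

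At φ = 0.10 power is about 77%. Correct while-on-treatment incidence at f = 20% (6.00 against 3.00) gives v = 48.0, a standard error of 0.274 and Φ(0.54) ≈ 71%. Changing the estimator therefore does not recover the power.

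**Unequal starts.** Suppose instead that every event follows worsening, that half of worsening patients have an event, and that 50% of worsening placebo patients start against 25% on active. Simulation with all starters censored then gives a difference of about 1.1 points and a ratio of 0.72. This marks how far the result could move and is not a forecast.

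**The case against.** The strongest reply is that little follows in practice.

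1. **The shrinkage is measured against a strategy the table does not name.** This stands. Against while-on-treatment, Kaplan-Meier with all starters censored is high by under 0.1 point in this range, and the correct competing-event estimate would be slightly smaller still.
2. **Rule 4 censors only starters who stay event-free, and rule 1 counts the rest.** This also stands. A reader might infer that patients heading for hospital are dropped just before their event; the table as worded does not do that. Any shrinkage then depends on rescue working, and with no rescue efficacy there is none. But under this wording, whether a starter is censored depends on the future outcome, and events after a start are used despite the restriction in Section 2.1.1.
3. **The risk ratio hardly moves.** True if start rules are equal across arms, which blinding supports. A reader might infer inflated type I error; nothing shown here supports that under equal start rules.
4. **There are safeguards.** The composite secondary strategy is a useful check but answers another question. Stratification captures the part of starting that tracks baseline risk, not the worsening itself. Text after Section 7.2.3 is missing from the public copy, so it cannot be said that no other sensitivity analysis was planned.
5. **Starts outside the rules can occur.** Section 3.3.4 foresees prohibited treatment, so not every start need follow worsening. Permitted ones do.

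**Conclusion.** The point holds as a mismatch between named strategy and estimator, with censoring that the protocol's own rescue rule makes informative. The text alone establishes that.

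The size rests on assumed start rates, timing and rescue efficacy. For f of 10% to 20%, the risk difference is about 3.4 to 3.05 points if every starter is censored, or about 3.6 to 3.4 as worded with 50% rescue efficacy, against a hypothetical 3.75. The ratio stays near 0.50 with equal start rules.

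A reader might infer a seriously wrong primary result, or that the primary estimate must be replaced by a weighted one. The documents support neither. The numerical effect is modest at these rates. At f = 20% there would be only about 641 × (0.075 × 0.20 + 0.925 × 0.02) ≈ 21 starters on placebo and 641 × (0.0375 × 0.20 + 0.9625 × 0.02) ≈ 17 on active, too few to rest the main analysis on a weighting model.

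No Phase III result was affected: the SAP reports that the study was discontinued with five patients randomised. This is a defect in the plan, and worth correcting in any design that reuses it.

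**What to change.** Choose one question and make Sections 2.1.1, 7.2.2 and 7.2.3 and Tables 7.2.2:1 and 7.3.1:1 agree with it.

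- **If while-on-treatment is kept:** estimate the Day 29 cumulative incidence of hospitalisation or death before start, with start of the product as a competing event (Aalen-Johansen), and use the matching variance in place of Greenwood's. Reconcile rules 1 and 4 with Section 2.1.1, so that the handling of an event after a start is stated once.
- **If the effect without other products is intended:** name the strategy hypothetical and state the independent-censoring assumption. Make rules 1 and 4 treat starters alike whatever happens to them later. Prespecify a sensitivity analysis with inverse-probability-of-censoring weights, using a parsimonious model and truncated weights. Data already scheduled would serve: risk group, serology, WHO score, and diary temperature and oxygen saturation. Report it beside the planned composite analysis.

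Neither option changes a treatment rule, a visit or the number of patients. The cost is protocol and SAP wording and a little more analysis work. The weighted analysis will have a wider interval and may be unstable if starters are few, which is why it belongs in a sensitivity role.
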